Design	
This study will provide rigorous epidemiologic evidence regarding the influence of fetal exposure to HIV and ART on developmental and mental health outcomes from infancy to adolescence using the following study designs: Longitudinal cohort study, cross sectional assessments and costing and implementation surveys. Accrued data will be disseminated in a stakeholder workshop conducted in the last year of the study.
 
To do this we will enroll a longitudinal cohort of HIV exposed uninfected (HEU) and HIV uninfected (HUU) infants and follow them up 6 monthly with extended follow-up to 4 years. Assessments will include growth, hearing and neurodevelopment (Aim 1a) and telomere length (Aim 1b).
 
In Aim 2, we will utilize a cross-sectional study design to pilot test mobile screening strategies to detect neurodevelopmental and mental health outcomes in HEU (Aim 2a). Pilot results will inform the implementation of a larger population based cross-sectional assessment of HEU outcomes (Aim 2b).
 
In aim 3, we will estimate the cost of the screening strategies and convene a stakeholder workshop to review data regarding programmatic integration of HEU screening.

Population	
Aim 1: HEU and HUU infants age 6 weeks and their mothers
 
Aim 2: HEU and HUU children and adolescents age 3-18 years and their caregivers
 
Aim 3: Abstracted records of cost information, Stakeholders in pediatric and adolescent health, health care workers (HCW), policy makers

Sample size	
Aim 1: 2000 mother-infant pairs, 1000 HEU and 1000 HUU
 
Aim 2: Pilot phase: 200 HEU and 200 HUU and their caregivers, Population based assessments: 4000 caregiver-child HEU pairs, 400 caregiver-child HUU pairs
 
Aim 3: 25-50 HCW, policy makers and stakeholders in pediatric health

Study sites:	
Aim 1: 5 public sector maternal and child health (MCH) clinics, 2 in urban Nairobi (Mathare, Kenyatta National Hospital) and 3 rural MCH clinic sites (Homa Bay, Kisumu, and Rachuonyo).
 
Aim 2: Pilot phase: Rachuonyo sub-county hospital. Population based assessments: 100 large HIV care clinics throughout Kenya
 
Aim 3: Workshop will be concerned in Nairobi/Western Kenya

Study Duration:	5 Years

8. Background

Maternal HIV and antiretroviral exposure may be potential fetal determinants of mental health

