Child or adolescent age 3-18 years

Child/adolescent is healthy and HIV negative

Mother HIV status known

Mother HIV diagnosis and ART timing known (for HEU)

Caregiver \geq 18 years willing to take children to clinic for evaluation

iv. Enrollment and study procedures

Enrollment will be conducted at a neutral location (typically public MCH clinic) or at home. No additional visits will be conducted after enrollment.

Determination of HIV status for HEU and HUU: A combination of medical records and HIV testing will be used to determine HIV status of mothers and children. Maternal HIV-positive status during the pregnancy with each child will be determined first using the mother-baby maternal and child health booklet; in the event that this

HOPE study protocol

Version 1.3

July 21, 2020

booklet is not available, records from the HIV care clinic documenting the date when the mother was diagnosed with HIV or started ART will be used (only for HIV positive mothers). In the event of no records are available, maternal report of being diagnosed with HIV either during or prior to the pregnancy with each child will be used (only for HIV positive mothers). For mothers who report not being HIV positive at the time of pregnancy and for whom mother-baby maternal and child health booklets are not available, we will offer maternal HIV testing; mothers who do not consent to HIV testing will not be enrolled.

For HEU dyads, children's HIV negative status will be determined using the same set of procedures (first reviewing mother-baby maternal and child health booklet, then infant HIV testing history records); if the child has not been tested for HIV after the cessation of breastfeeding, HIV testing will be offered for the child. Children ages 7-14 years will be asked to provide assent without mention of HIV; children ages 15-18 will be asked to provide assent (or consent for 18 year olds) with explicit mention of HIV testing and will be told that they can choose whether they wish to share their results with their caregivers. If children decline HIV testing, they will not be enrolled in the study.

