We will conduct a micro-costing study to determine the total cost of screening HEU in Kenya for growth, cognitive delays, and mental health. To collect costs, detailed cost information will be obtained from local, county and national level; these do not include human subjects and are not further described in this protocol. In addition to the non-human subjects cost collection elements, we will conduct time and motion studies with health care workers to assess the time spent delivering and receiving services; this set of activities is described below as time-and-motion data collection.

Additionally, we will convene a 2-day stakeholder workshop at the end of the study period to disseminate results and envision a screening program.

ii. Study populations

Caregivers: caregiver to a child receiving screening in Aims 1 or 2, ≥ 18 years of age

Health care workers (for costing): ≥ 18 years, delivering screening services within Aims 1 or 2; may be study staff or non-study staff

Health care workers (for stakeholder workshop): ≥ 18 years, has experience working in a health facility in Kenya

HOPE study protocol

Version 1.3

July 21, 2020

Stakeholders: >=18 years, involved in informing decision-making for ministries of health or related organizations

iii. Recruitment procedures

Time-and-motion: We will invite caregivers and health care workers within Aims 1 & 2 to learn about additional elements of this study at the end of their study visits. They will be invited to participate in time-and-motion data collection, assessing the duration of time they spend delivering and receiving screening assessments, and their salaries (to estimate costs). For HCW we will also invite them to provide information on the hypothetical impact of additional screening activities on their ability to deliver other routine services.

Stakeholder workshop: Health care workers, policy makers and stakeholders in pediatric health in Kenya will be purposively recruited to participate in a 2 day workshop on child/adolescent mental health screening in program setting. They will be informed that during the workshop, the study team will present data from Aims 1 and 2, and brainstorm on screening tools, structure and components of an integrated HEU screening program in Kenya.

iv. Enrollment and study procedures

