Time-and-motion: Interested caregivers and HCW will complete an oral informed consent to participate in time-and-motion data collection. They will note the time when services began and ended, their salaries, and the HCW will report on the hypothetical impact on service delivery.

Stakeholder convening and dissemination: We will convene a 2-day stakeholder workshop in the last 3 months of the study period. Invited participants will include policy makers in PMTCT, pediatric and adolescent HIV (drawn from the Kenya National AIDS and STI Control Program [NASCOPI]), members of the National Pediatric HIV Technical Working Group, HIV care partners), policy makers in child development including ECD and from the Ministry of Education, child health partners (UNICEF, World Bank), health care workers in MCH and HIV care settings in Kenya, caregivers of HEU (drawn from existing networks of PLHIV) and HEU adolescent representatives. The guest list will be reviewed with Ministry of Health partners to ensure relevant stakeholders are included. We have conducted similar meetings for the development of a national disclosure and transition framework and tools and therefore have experience convening these meetings. The purpose of the meeting will be to: 1) present results of the study regarding burden of neurodevelopmental and mental health outcomes in HEU and HUU, and evidence for elevated risk in HEU or subgroups of HEU at-risk, 2) discuss experience recruiting HEU cohorts and potential for scale-up, 3) discuss experience with, and cost of, screening tools and potential integration within existing health services, 4) brainstorm on structure, components and outcomes of an integrated HEU screening program in Kenya. The discussions will be audio recorded and information on the process written up into a publishable manuscript.

v. Laboratory methods

N/A

vi. Data collection instruments

Time-and-motion survey including time spent, salary, and hypothetical impact on clinical duties

Stakeholder meeting notes about brainstorm on structure, components and outcomes of an integrated HEU screening program in Kenya.

HOPE study protocol

Version 1.3

July 21, 2020

vii. Data analysis

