Cost data collection and analysis methods: We will estimate the costs of conducting screening for growth deficits, hearing deficits, cognitive delays, and mental health for children in each age stratum defined in Aim 2. In addition to the cost per child screened in each age stratum for each condition, we will quantify the cost per child who screens positive and is referred for subsequent either diagnostic or management services. Costs to be collected and data sources are noted in Table 12. We will conduct a detailed, in-country micro-costing using primary data from study budget records, expense reports, and interviews with program staff to understand resource utilization. We will also utilize secondary cost data from literature, health facilities, and county health expenditure reports. We will conduct time-and-motion observation to estimate time spent by health care providers and clients on conducting each of the screening assessments and assess how these tasks impact their regular clinical duties. We will follow the principles outlined in the Global Health Cost Consortium Reference Case ¹⁷⁶ and the International Society for Pharmaceutical and Outcomes Research’s guidance on costing analyses ¹⁷⁷. We will take a payer perspective for this analysis.

Table 12: Micro-costing components and estimation approach		
Cost	Cost type	Estimation approach
Start up costs		
Micro-planning	Fixed	Project budget abstraction
Screening test licensing fees	Fixed	Project budget abstraction
Training	Fixed	Project budget abstraction
Tablets	Fixed	Project budget abstraction
Recurrent costs		
Personnel		
HCW time (service provision)	Variable	Quantity: Time-and-motion studies at select facilities
HCW time (record keeping)	Variable	Unit cost: HCW salaries from records
HCW time (supervision)	Fixed	Quantity: Time-and-motion studies at select facilities
Caregiver time during screening	Variable	Unit cost: Caregiver salaries from surveys
Transportation		
HCW transportation	Variable	Transportation costs from surveys
Caregiver transportation	Variable	
Facilities & overhead		
Space costs	Fixed	Estimated based on square footage at nearby commercial property value
Airtime & data	Variable	Project budget abstraction

viii. Training procedures

Staff will be trained on data collection for time in motion surveys. A senior study staff or co-investigator will summarize discussions at the stakeholder meeting.

13. Quality assurance procedures

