Pitfalls and alternative strategies: The Aim 1 cohort is designed to be homogeneous – with all HEU having initiated ART either before or during pregnancy and all enrolled contemporaneously at 6 weeks of age, which accommodates secular trends in comparisons with the HUU cohort. HUU will be recruited from the same MCH clinic as HEU, which ensures that mothers reside in the same community, and thus have similar sociodemographic characteristics; this attenuates risk for confounding in comparisons between HEU and HUU. We will not enroll during pregnancy, which will under-ascertain perinatal morbidity and preterm birth. However, we have access to 3 ongoing birth cohorts that are accruing pregnancy-enrolled HEU and HUU. Data from those cohorts complement this study, which is designed to be a population-based multi-site urban/rural cohort.

17. Timeline

Timeline: In the first 6 months we will obtain study approval, recruit and train staff and establish study sites. We anticipate to complete enrollment for the longitudinal cohort in the second half of year 1. Aim 2 pilot will begin in the second half of year 1 and be complete in 10 months. Aim 2 population surveys will begin after the pilot in the second half of year 2. Aim 3 activities will be conducted in year 4-5.

Study Timeline					
	Year 1	Year 2	Year 3	Year 4	Year 5
Study approvals, training	■				
Aim 1 Enroll longitudinal cohort		■			
Follow-up longitudinal cohort		■	■	■	■
Aim 2 Pilot cross-sectional cohort		■	■		
Aim 2 Population based assessments			■	■	
Aim 3 Cost analysis				■	■
Aim 3 Stakeholder meeting					■

18. Human subjects

a) Ethical Approval

We will obtain ethical approval from the University of Washington (UW) Human Subjects Division (IRB) and Kenyatta National Hospital-University of Nairobi (KNH-UoN) Ethics and Research Committee (ERC). There will be minimal risk to the participants taking part in this study. Any changes to the protocol will be submitted to the UW IRB and KNH-UoN ERC.

b) Collaborating sites

The study will be conducted in collaboration with the UW, KNH, and UoN. The study will be reviewed by the KNH ERC and UW IRB and will not be started before approvals are obtained from all two organizational review boards.

c) Informed Consent

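### Aim 3 describes two incompatible ways of measuring screening time: self-noted start and end of services by participants invited after the visit, and observation of each assessment for the costing

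*Protocol*

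**What the plan says.** All references are to the Protocol.

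- **Section 12.e.ii (Aim 3 study populations).** Eligible health workers are those "delivering screening services within Aims 1 or 2; may be study staff or non-study staff".
- **Section 12.e.iii (Aim 3 recruitment).** The invitation goes to caregivers and health workers "within Aims 1 & 2 to learn about additional elements of this study at the end of their study visits". The section describes the data as the time spent giving and receiving screening assessments.
- **Section 12.e.iv (Aim 3 procedures).** Those who consent record the times themselves: "They will note the time when services began and ended".
- **Section 12.e.vi (Aim 3 instruments).** The survey is described in one line that covers duration, pay and the supposed effect on other work. It names no tool, condition or age stratum.
- **Section 12.e.vii (Aim 3 analysis).** The output is a cost per screened child, split by condition and by Aim 2 age stratum. Its basis is different: "We will conduct time-and-motion observation to estimate time spent by health care providers and clients on conducting each of the screening assessments". Table 12 takes health-worker time from studies at selected facilities.
- **Section 12.d.iv (Aim 2 procedures).** Aim 2 is a single contact: "No additional visits will be conducted after enrollment".
- **Section 17 (Timeline).** "Aim 3 activities will be conducted in year 4-5".

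**The concern.** The procedures and the analysis differ on two things: who records the time, and at what level. Self-noted times for services are not the same data as observed times for each assessment, and only the second kind leads directly to a cost per condition.

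The order of events adds to this. Someone invited once the screening is over cannot note its start prospectively. For a participant with only one visit, recall is all that is left.

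The calendar matters too. Aim 3 starts well after Aim 2 screening begins, and Aim 2 is the only source of screening times for older children.

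At stake are the time quantities behind the cost per condition and stratum, which the stakeholder workshop is to use when it discusses the cost of the screening tools and their integration into services. A visit that was not timed when it took place cannot be timed later.

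**Working it through.** The plan gives no figure to reproduce. The check sets the sections side by side and adds simple arithmetic.

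**1. Who can be timed prospectively under the recruitment and procedures sections?**

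| Participant | Contacts | If invited at the end of a visit |
|---|---|---|
| Aim 2 caregiver | 1 (section 12.d.iv) | Recall only |
| Aim 1 caregiver | 9: enrollment plus months 6, 12, 18, 24, 30, 36, 42, 48 (Aim 1 data collection table) | Later visits can be timed |
| Health worker, Aim 1 or 2 | Many children | Later children can be timed |

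The recall problem is therefore confined to Aim 2 caregivers.

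**2. Can Aim 1 stand in for Aim 2?** Aim 1 plans to enroll infants at 6 weeks and "follow them up 6 monthly with extended follow-up to 4 years". Its children reach only the lower end of the 3-6 stratum. The 7-10, 11-14 and 15-18 strata depend on Aim 2 alone.

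**3. What would a single start and end per visit contain?** Planned minutes for a child of 7-10, from the tool table in section 12.d.vi:

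- Hearing: HearScreen 5
- Cognition: NIH Toolbox 25-30
- Mental health: SDQ 10 + SNAP-IV 5-10 = 15-20
- Total: 5 + 25 + 15 = 45, to 5 + 30 + 20 = 55
- With MINI-KID (10) after a positive screen: 55-65

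One total cannot be divided into three conditions without outside information. Dividing it by the planned minutes would put the plan's assumed durations in place of measurements. It would also leave out growth, because the tool table gives no duration for anthropometry.

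**4. When does Aim 3 overlap with Aim 2?** Months are counted from study start, using section 17.

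- Pilot: starts in the second half of year 1 (months 6-12) and lasts 10 months. End = 6 + 10 to 12 + 10 = months 16-22.
- Aim 3: starts with year 4, at month 36. The pilot is over 36 − 22 = 14 to 36 − 16 = 20 months earlier.
- Population survey: starts in the second half of year 2 (months 18-24). The text gives no end. With end month T, overlap = max(0, T − 36).
  - T = 48 (the timeline table as extracted marks years 3 and 4): 12 months of overlap.
  - T ≤ 36: none.

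The extracted table is weak evidence. Its Aim 1 enrollment and pilot rows fall later than the text says, so its columns may have shifted when the PDF was read.

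**The case against.** The strongest defence is that the sections can be read together. Section 12.e.iii speaks of time spent on screening assessments, section 12.e.vii specifies observation of each one, and section 12.e.viii trains staff to collect the data. On that reading, services in section 12.e.iv means each screening service. The form itself is not shown, so it cannot be said to lack fields for each tool. This stands as a possible reading. It does not settle who records the time, and it leaves the invitation after the visit unexplained.

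The defence also notes that staff time is the input that matters most under the stated payer perspective, that caregiver time is a separate row in Table 12, and that health workers can be timed on later children. This stands, and it limits the recall problem to caregivers in Aim 2.

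A reader might go further in three ways that the documents do not support:

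- **That the promised costs cannot be produced at all.** Health-worker timing in year 4 could cover every stratum if the surveys are still running, and Aim 1 caregivers have further visits.
- **That most Aim 2 visits being untimed is itself a defect, or that recall error swamps the short tools.** Table 12 plans a sample at selected facilities, and unit times do not need every visit. The Protocol gives no figure for recall error, and an error in a recalled whole-visit time should not be set against the length of a single tool.
- **That timing practised teams late in the study understates programme cost.** This is not shown. Table 12 costs training and other start-up items separately from recurrent staff time.

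**Conclusion.** The inconsistency is real and should be resolved. Sections 12.e.iii and 12.e.iv describe times noted by participants who were approached after the visit. Section 12.e.vii depends on observed times for each assessment. Followed literally, the procedures give recalled times from Aim 2 caregivers. If one start and end per visit is meant, they give totals that do not separate the conditions.

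On timing, the pilot cannot be measured prospectively under section 17. For the three strata above age 6, prospective timing rests on the population survey still running in year 4, with an overlap between 0 and about 12 months depending on an end date that the text does not state.

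The conclusion assumes that Aim 3 starts no earlier than year 4 and that the invitation does come at the end of the visit. It does not touch the Aim 1 or Aim 2 comparisons, and it does not show that the Aim 3 costs would be biased in a known direction. It is a cheap improvement rather than a serious flaw.

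**What to change.** Reconcile sections 12.e.iii, 12.e.iv, 12.e.vi and 12.e.vii so that they describe one method:

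1. Record time for each assessment, with a start and a stop field for each tool on the existing REDCap or tablet forms during Aim 2 screening. This can be at all visits or only at the selected facilities. Summarise by tool and age stratum.
2. Obtain time-and-motion consent before the timed visit.
3. State in section 17 that time recording runs while Aim 2 screening is under way, and give the planned end of the population survey.
4. Keep the year 4-5 survey for salaries, for record-keeping and supervision time (which tool timestamps do not capture), and for the effect on routine duties.

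The cost is a few form fields and a short change to the consent and data-collection text. No extra staff or visits are needed, because data already go into REDCap and tablet-based tests are already planned. The drawback is that timestamps include short interruptions, so medians should be reported as well.
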